16.3.3 Correlative Analyses

16.3.3.1 Patients will complete the Expanded Prostate Cancer Index Composite short form (EPIC-26) questionnaire at baseline and at the specified post-treatment time points as shown Section 4.0. Subdomains for urinary, bowel, and sexual function will be evaluated at each time point and summarized descriptively. Changes across time will be evaluated to assess patient function and quality of life after study treatment.

16.3.4 Over Accrual: If more than the target number of patients are accrued, the additional patients will not be used to evaluate the stopping rule or used in any decision making processes; however, they will be included in final endpoint estimates and confidence intervals.

16.4 Data & Safety Monitoring:

16.4.1 The principle investigator(s) and the study statistician will review the study at least twice a year to identify accrual, adverse event, and any endpoint problems that might be developing. The Mayo Clinic Radiation Oncology Data Safety Monitoring Board (DSMB) is responsible for reviewing accrual and safety data for this trial at least once a year, based on reports provided by the statistical office.

16.4.2 Adverse Event Stopping Rules: The stopping rules specified below are based on the knowledge available at study development. We note that the Adverse Event Stopping Rule may be adjusted at any time during the conduct of the trial and in consideration of newly acquired information regarding the adverse event profile of the treatment(s) under investigation. The study team may choose to suspend accrual if there are unexpected adverse event profiles that have not crossed the specified rule below.

Accrual will be temporarily suspended, if at any time we observe events considered at least possibly related to study treatment (i.e. an adverse event with attribute specified as “possible,” “probable,” or “definite”) that satisfy one of the following:

- If 4 or more patients in the first 20 treated patients experience a grade 3 or higher GI or GU adverse event at least possibly related to treatment at any time and after 3 months following completion of the protocol treatment
- After the first 20 patients have been treated: if $\geq 20\%$ of all patients experience a grade 3 or higher GI or GU adverse event at least possibly related to treatment at any time after 3 months following the completion of protocol treatment.

In addition, we will review grade 4 and 5 adverse events deemed “unrelated” or “unlikely to be related”, to verify their attribution and to monitor the emergence of a previously unrecognized treatment-related adverse event.

16.6 Results Reporting on ClinicalTrials.gov: At study activation, this study will be registered within the “ClinicalTrials.gov” website. The Primary and Secondary Endpoints along with other required information for this study will be reported on ClinicalTrials.gov. For purposes of timing of the Results Reporting, the initial estimated completion date for the Primary Endpoint of this study is 3.5 years after the study opens to accrual. The definition of “Primary Endpoint Completion Date” (PECD) for this study is at the time the last patient registered has been followed for at least 2 years.

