2.2 Secondary

- 2.2.1. Late grade ≥ 2 GI and/or GU toxicities of interest within 24 months after the protocol RT, using the CTCAE v4.0.
- 2.2.2. Acute grade ≥ 3 GI and/or GU toxicities of interest during and within 3 months after the protocol RT, using the CTCAE v4.0.
- 2.2.3. Disease-free survival including freedom from PSA relapse at 5 years
- 2.2.4. Disease-specific survival at 5 years
- 2.2.5. Overall survival at 5 years

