The investigator will review all adverse event reports to determine if specific reports need to be made to the IRB and FDA. The investigator will sign and date the adverse event report when it is reviewed. For this protocol, only directly related SAEs/UPIRTSOs will be reported to the IRB.

10.4 CTCAE v4.0 is used for the following AEs to be graded at each evaluation and pretreatment symptoms/conditions to be evaluated at baseline:

System Organic Class	Adverse events/Symptoms
Gastrointestinal	Diarrhea
	Fecal incontinence
	Proctitis
	Rectal hemorrhage
	Rectal ulcer
	Small intestinal obstruction

	Stricture/Stenosis: Rectum
Renal/Genitourinary	Bladder spasm
	Hematuria
	Urinary frequency
	Urinary incontinence
	Urinary tract obstruction
	Urinary tract pain
	Urinary urgency
	Cystitis noninfective
	Urinary retention
Sexual/Reproductive function	Erectile dysfunction

Acute AEs are defined as those that occur from day 1, or commencement of radiation therapy, through 3 months after the completion of protocol treatment.

All AEs seen after 3 months after the completion of protocol treatment are considered late effects.

10.4.1 Submit via appropriate reporting mechanisms (i.e., paper or electronic) the following AEs experienced by a patient and not specified in Section 10.4:

Grade 5 AEs (Death)

10.4.1.1.1 Any death within 30 days of the patient's last study treatment or procedure regardless of attribution to radiation treatment

10.4.1.1.2 Any death more than 30 days after the patient's last study treatment or procedure that is felt to be at least possibly related to radiation treatment must also be submitted as a Grade 5 AE, with a CTCAE type and attribution assigned.

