16.2.2 Sample Size: This study is expected to require a maximum of 51 evaluable patients. We anticipate accruing 5 additional patients to account for ineligibility, cancellation, major treatment violation, or other reasons. Therefore, this study is expected to accrue a maximum of 56 patients overall.

16.2.3 Accrual Rate and Study Duration: The anticipated accrual rate is approximately 3-4 patients per month. Therefore, the accrual period for this phase II study is expected to be approximately 1.5 years. The final analysis can begin as soon as the last patient has been observed for 2 years, or at approximately 3.5 years after the study opens to accrual.

16.2.4 Assuming that the number of late grade 3 or higher GI or GU toxicities is binomially distributed, with a significance level of 10%, the probability of declaring that the regimen warrants further studies (i.e., statistical power) under various toxicity proportions can be tabulated as a function of the true toxicity proportion as shown in the table below.

If the true late toxicity rate is...	0.20	0.15	0.10	0.05
--------------------------------------	------	------	------	------

Then the probability of declaring that the regimen is promising and warrants further study is...	0.02	0.10	0.41	0.89
--	------	------	------	------

16.2.5 Other considerations: Adverse events, quality/duration of response, and patterns of treatment failure observed in this study, as well as scientific discoveries or changes in standard care will be taken into account in any decision to terminate the study

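### The two mandatory accrual-suspension bullets in Section 16.4.2 do not match: it is unclear whether acute grade 3+ GI/GU events count, and a late-only rule sees little data before accrual closes

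*Combined protocol and SAP*

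**What the plan says.** Section 16.4.2 gives two conditions under which accrual will be temporarily suspended. Both are limited to events at least possibly related to treatment.

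- **Bullet 1:** "If 4 or more patients in the first 20 treated patients experience a grade 3 or higher GI or GU adverse event", with the time window "at any time and after 3 months following completion of the protocol treatment".
- **Bullet 2:** once 20 patients have been treated, 20% or more of all patients with such an event "at any time after 3 months following the completion of protocol treatment".

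The same section adds discretion: "The study team may choose to suspend accrual if there are unexpected adverse event profiles that have not crossed the specified rule below". It also allows the rule to be adjusted during the trial. Under Section 16.4.1 the investigators and statistician "will review the study at least twice a year to identify accrual, adverse event, and any endpoint problems that might be developing", and the DSMB reviews safety at least yearly.

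Goal 2.2.2 covers acute grade 3+ "GI and/or GU toxicities of interest during and within 3 months after the protocol RT". Section 16.3.2.4 estimates that rate with an exact interval but attaches no threshold. Section 10.4 defines the acute period: "Acute AEs are defined as those that occur from day 1, or commencement of radiation therapy, through 3 months after the completion of protocol treatment". Section 16.2.3 states that "the accrual period for this phase II study is expected to be approximately 1.5 years".

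**The concern.** The suspension is mandatory, so staff need to know which events count. Bullet 2 excludes acute events. Bullet 1 either has a stray word and means the same, or counts acute events as well. Neither reading is comfortable. If late only, no number of related acute grade 3–5 GI/GU events obliges a pause. If acute events are included, they count among the first 20 patients and then stop counting under bullet 2, with no reason given.

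Timing adds to this. The only action is to suspend accrual, and accrual is short compared with the period in which late events appear. Acute events are the toxicity that can be largely seen while a pause could still protect patients not yet enrolled. Section 1.3 notes that this simultaneous hypofractionated proton approach had not been studied prospectively.

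The anchor is a further problem. Both bullets count from completion of protocol treatment, and Section 7.0 defines protocol treatment to include androgen deprivation, for 28 months outside intermediate-risk disease.

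**Working it through.** **The plan's own figures.** The documents give operating characteristics for the final decision only. P(4 or fewer of 51) at true rates 0.20, 0.15, 0.10 and 0.05 is 0.016, 0.102, 0.413 and 0.890, which matches the printed 0.02, 0.10, 0.41 and 0.89 (Section 16.2.4). No figures are given for the suspension bullets.

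**Inputs.** 56 patients at 3–4 per month (16.2.2, 16.2.3); 5 weeks of RT, or 1.15 months (1.4); 0–1 month from enrolment to start (3.2.8); late window from 3 to 24 months after proton therapy, or 21 months (16.3.1.1). Assumptions: even accrual, no dropout, late onset uniform over the 21 months.

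**Exposure at last enrolment.** With r patients per month, accrual ends at T = 56/r, which is 14 to 18.7 months. The late window opens L = wait + 1.15 + 3 = 4.15 to 5.15 months after enrolment. Patient i has observed late time w_i = max(0, T − i/r − L).

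- First 20, least favourable case (r = 4, wait 1): mean w = 14 − 5.15 − 10.5/4 = 6.2 months; 6.2/21 = 30%.
- First 20, most favourable case (r = 3, wait 0): mean w = 18.67 − 4.15 − 10.5/3 = 11.0 months; 11.0/21 = 53%.
- All 56: 35 patients in the window averaging 4.35 months gives 35 × 4.35/(56 × 21) = 13%; 43 patients averaging 7.2 months gives 26%. Nobody has completed the window.

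**Chance that a late-only bullet 1 fires before accrual ends.** Each of the first 20 has probability p × w_i/21 of an observed event. P(4 or more) is the tail of the sum of these independent events.

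| True late rate p | r = 4, wait 1 | r = 4, wait 0 | r = 3, wait 1 | r = 3, wait 0 |
|---|---|---|---|---|
| 15% | 1.1% | 1.8% | 5.0% | 6.7% |
| 20% | 2.8% | 4.4% | 11.7% | 15.1% |

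The fair comparator is the same count with complete follow-up: P(4 or more of 20) = 35% at 15% and 59% at 20%. Even full data would trigger only 59% of the time at 20%, because 20% is the threshold itself. The fall from 59% to 3–15% is the effect of timing. Bullet 2 adds almost nothing. In simulation with accrual over 14 or 18 months it fired before accrual closed in at most 1.6% of trials, even at a true rate of 40%. Its denominator, taken there as all treated patients, includes men not yet in the late window.

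**When acute data arrive.** The 20th patient passes 3 months after RT at 20/r + L, which is month 9.2 (20/4 + 4.15) to month 11.8 (20/3 + 5.15). Across the four scenarios 16 to 24 patients are then still to enrol.

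**What an acute 4-in-20 count would do.** Exact binomial P(4 or more of 20):

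| True acute rate | 4.3% | 10% | 15% | 20% | 30% |
|---|---|---|---|---|---|
| Chance of a pause | 1.0% | 13% | 35% | 59% | 89% |

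The 4.3% is the acute grade 3 GU rate in Table 3. The other rates are assumptions, since the documents set no acceptable acute rate.

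**The anchor, read literally.** With 28 months of androgen deprivation started 2 months before RT (Section 7.2 calls this usual), protocol treatment ends 28 − 2 − 1.15 = 24.85 months after RT. The bullets would then start counting at 24.85 + 3 = 27.85 months. That is after the 24-month primary window and after accrual has closed.

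**The case against.** A reader might infer that the rules count only late events, that acute toxicity cannot trigger a pause, and that the discretionary clause is the sole protection. The documents do not support any of these. Bullet 1 can be read to include acute events. The study team may suspend accrual without a crossed rule, and the rule itself may be changed. Safety is reviewed at least twice yearly by the investigators and statistician and yearly by the DSMB. Section 8.0 allows treatment to be interrupted for acute grade 3+ events. Serious events follow the sentinel event procedure (10.5.1), unanticipated problems reach the IRB within 5 working days (10.3.1.1), and any death within 30 days of the last study treatment is submitted regardless of attribution (10.4.1). All of this stands. None of it, however, is a mandatory pause in accrual, and one or two reviews a year is sparse against 14–18.7 months of accrual.

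A late focus also has a stated rationale. Section 1.5 calculates a lower acute-tissue BED than the conventional schedule (85.7 versus 93.5) and identifies late injury as the risk. The photon study of the same schedule saw no acute grade 3 GI and no grade 4 events (Table 3). Having no acute rule could therefore be a defensible choice, but the plan does not say it was made, and bullet 1 leaves it open.

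Nor should the cost of an acute trigger be put at 1%. That rests on one point estimate: 4.3% of 97 is about four men, and an exact 95% interval for 4 of 97 runs from about 1% to 10%. Grading there was by CTCAE v3.0, not v4.0.

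**Conclusion.** The point holds as an inconsistency and a gap that should be closed, not as an absence of safety oversight. The bullets conflict on whether acute events count. On the late-only reading, acute grade 3+ GI/GU toxicity has no mandatory numeric trigger. On that same reading, and with the window counted from the end of proton therapy, the rules would fire before accrual closes in about 3–15% of trials at a true late rate of 20%, and about 1–7% at 15%, the rate the plan calls unacceptable.

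The exposure fractions follow from the plan's accrual and treatment times. The firing probabilities also depend on uniform onset, which the documents neither state nor contradict: earlier onset would raise them, later onset would lower them. The choice of an acute threshold remains the sponsor's.

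**What to change.** In Section 16.4.2:

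1. Give both bullets the same time window and state whether acute events count. The documents do not show which meaning of bullet 1 was intended, so the sponsor must decide.
2. Anchor the late window to completion of proton beam therapy, as Section 16.3.1.1 does. Say which patients form the denominator of bullet 2.
3. Add an explicit accrual-review trigger for related grade 3+ GI/GU events from the start of RT through 3 months after it, with a threshold set by the sponsor and its operating characteristics shown. The plan's own 4-in-20 is one option, with the pause probabilities tabulated above.

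The cost is protocol wording. Section 4.0 already schedules toxicity assessment weekly during RT, at its end and at month 3, so no new data are needed. The downside to state is an unneeded temporary pause: with 4-in-20, about 1% at an acute rate of 4.3%, but 13% at 10% and 35% at 15%. A trigger on acute events does not speed up the late rule. The plan should acknowledge that the late rule can do little before enrolment is complete.

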1.4 Study proposal

In the proposed study, the prostate +/- seminal vesicles will be treated with a hypofractionation regimen using daily 2.7 Gy fractions to 67.5 Gy, while the regional pelvic lymph nodes will be simultaneously treated with daily 1.8 Gy fractions to 45 Gy, using proton beam therapy. Assuming a α/β value of prostate carcinoma between 1.5 and 3 Gy, 67.5 Gy in 2.7 Gy fractions is equivalent to 80.2 Gy to 85.9 Gy in 1.8 Gy fractions. The overall treatment time is 5 weeks, which is about 3.8 weeks shorter than the standard conventional dose fractionation schedule (44 fractions over 8.8 weeks). A high precision RT technique using pencil beam proton therapy and daily on-line targeting of the prostate gland is employed to minimize the dose to adjacent normal organs (bladder, rectum, and small bowel), which will, in turn, reduce the risk of radiation toxicity.

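### The second accrual-suspension bullet in 16.4.2 divides late events by all patients, so its 20% line works as about 26–46% of men at risk and it adds little to the first bullet

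*Combined protocol and SAP*

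**What the plan says.** Section 16.4.2 gives two conditions. Either one temporarily suspends accrual.

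- First bullet: "If 4 or more patients in the first 20 treated patients experience a grade 3 or higher GI or GU adverse event" that is at least possibly related and falls after the three-month mark. The cohort is fixed and no end date is given.
- Second bullet: it opens with "After the first 20 patients have been treated" and suspends if at least 20% "of all patients experience a grade 3 or higher GI or GU adverse event at least possibly related to treatment at any time after" three months from completion of protocol treatment.

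The lead-in makes these alternatives, either of which may be met at any point. The same section lets the team suspend accrual for unexpected toxicity that has not crossed the rule.

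Section 10.4 fixes the start of the late window: "All AEs seen after 3 months after the completion of protocol treatment are considered late effects". Nothing limits the second bullet's denominator to men who have reached that window. Section 16.3.1.1 does not help, because it makes a man evaluable for late toxicity once he has begun treatment, with no minimum follow-up.

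**The concern.** The numerator and denominator describe different groups. A man on radiotherapy, or two months past it, adds one to the denominator and cannot add to the numerator. While accrual is open there are always such men, so the observed percentage is biased low in exactly the period when the rule is meant to act. At stake is how many further men are treated before a pause, if late grade 3 or higher toxicity is well above the 5% that the plan hypothesizes. The mismatch is separate from whether 20% is the right level, and it would remain if that level were changed.

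**Working it through.** **The plan's own figures.** The plan gives no operating characteristics for the suspension rule. Its only tabulated probabilities (16.2.4) concern the final rule, 4 or fewer events in 51. The exact binomial gives 0.016, 0.102, 0.413 and 0.890 at true rates 0.20, 0.15, 0.10 and 0.05, against the stated 0.02, 0.10, 0.41 and 0.89. That table is correct and is not affected here.

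**Inputs.** Section 1.4: "The overall treatment time is 5 weeks". Section 10.4: late events start 3 months after treatment, counted here from the end of radiotherapy. Section 16.2.3: "The anticipated accrual rate is approximately 3-4 patients per month", and "the accrual period for this phase II study is expected to be approximately 1.5 years". Section 16.2.2: "Therefore, this study is expected to accrue a maximum of 56 patients overall". The last two give 56/18 = 3.1 a month, consistent with 3–4.

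**Men treated but not yet at risk.** Lag from start of radiotherapy = 35/30.44 + 3 = 1.15 + 3 = 4.15 months. Multiplied by the accrual rate, this is about 12.4 men at 3 a month, 14.5 at 3.5 and 16.6 at 4.

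**Effective threshold** = (0.20 × N, rounded up) / (N − men not yet at risk), for N treated:

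| N treated | Events needed | At 3 a month | At 4 a month |
|---|---|---|---|
| 25 | 5 | 5/12.6 = 40% | 5/8.4 = 60% |
| 30 | 6 | 6/17.6 = 34% | 6/13.4 = 45% (6/13 = 46% in whole men) |
| 40 | 8 | 8/27.6 = 29% | 8/23.4 = 34% |
| 51 | 11 | 11/38.6 = 28% | 11/34.4 = 32% |
| 55 | 11 | 11/42.6 = 26% | 11/38.4 = 29% |
| 56 | 12 | 12/43.6 = 28% | 12/39.4 = 30% |

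From 30 treated onward the range is about 26–46%. Rounding up to a whole event takes one point higher: 7/14.4 = 49% at 31 treated and 4 a month. Just after the 20th man, at 21 treated, the figure is 5/8.6 = 58% at 3 a month. At 4 a month the line cannot be reached there, since 5 events are needed from about 4 men.

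If the denominator means registered men, with the wait of up to 1 month that 3.2.8 allows, the lag is 5.15 months. The figures become 41–64% at 30 and 30–34% at 56.

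**What the second bullet adds to the first.** If the first bullet has not fired, at most 3 events lie in the first 20 men.

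- At 40 treated, at least 8 − 3 = 5 events must come from later men, of whom only 40 − 20 − 12.4 = 7.6 (3 a month) or 40 − 20 − 16.6 = 3.4 (4 a month) are at risk.
- At 56 treated, at least 12 − 3 = 9 must come from 23.6 or 19.4 men, which is 38% or 46%.

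So it seldom fires first.

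**Simulation.** Assumptions: 56 men, Poisson accrual at 3.5 a month, radiotherapy 0.5 month after registration, true late rate 30%, and onset spread evenly over the first 6, 9 or 21 months of the late window. The documents give no onset timing. Both bullets are taken to count late events only. The at-risk version of the second bullet needs at least 20 men at risk. Entries are the percentage of trials suspended before accrual closes; ranges and paired entries are repeat runs.

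| Onset window | Second bullet alone: as written | Second bullet alone: at-risk denominator | Both live: as written → at-risk denominator | Both live as written → at-risk, first bullet retired at 20 at risk |
|---|---|---|---|---|
| 6 months | 28–30 | 74 | 86.3 → 88.2; 87.2 → 88.0 | 86.6 → 74.8; 87 → 74 |
| 9 months | 12–14 | 50 | 77.4 → 78.1 | 76.8 → 48.7; 78 → 52 |
| 21 months | 0.1 | 3–4 | 21.6 → 21.7 | 21.6 → 2.8; 23 → 3 |

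At a true 20% rate with both bullets live, the change is 55.6 → 56.8, 44.1 → 44.4 and 7.5 → 7.5. Over all rates tried the gain is about 0–3 points. At a true 5% rate the second bullet alone fires in at most 0.2% of trials with either denominator.

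**The case against.** The strongest reply is that the second bullet is not the whole rule. The lead-in makes the bullets alternatives with no expiry. The first must outlast treatment of the 20th man to have any use: when he starts, only 20 − 16.6 = 3.4 to 20 − 12.4 = 7.6 men are in the late window. Read that way, the first bullet does most of the work and the denominator hardly matters. The principal investigators and statistician also review the study at least twice a year, the DSMB at least yearly (16.4.1), and the team may suspend at its discretion.

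Most of this stands. A reader might infer that the suspension rule as a whole stays silent at 30% late toxicity, or that the 28–30% against 74% contrast is the effect on this trial. The documents do not support either inference: those figures describe the second bullet acting alone, and the lead-in favours both acting together.

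Two things survive. The bullet still does not measure the percentage it appears to measure, and it is the only condition that covers men 21 to 56. Its opening words also allow a reading in which it takes over from the first bullet, which would leave the diluted condition as the only live one. Discretionary suspension is written for unexpected profiles, so it does not replace a stated rule on the primary safety outcome.

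**Conclusion.** The mismatch is real and follows from the wording plus the plan's own treatment time and accrual rate. From 30 treated onward the 20% line works as about 26–46% of men at risk, higher before that and about 26–30% near 56. It is not a constant, and it is slightly understated if men just past three months are regarded as only partly observed.

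The consequence depends on how the bullets combine. With both live throughout, correcting the denominator gains about 0–3 percentage points. Under a sequential reading, at a true 30% rate and 3.5 men a month, the rule would suspend in about 28–30% of trials with 6-month onset and 12–14% with 9-month onset. These simulated figures rest on assumed onset times; the threshold figures do not. The point is minor: worth correcting because it is a safety rule and cheap to mend, not because the trial is unprotected.

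**What to change.** In the second bullet of 16.4.2, replace the all-patients denominator with *all treated patients followed for at least 3 months after completion of proton beam therapy*, applied once at least 20 such patients exist. Count the events from the same point. This matches the primary endpoint in 16.1.1 and avoids doubt over whether protocol treatment, which Section 7.0 defines to include androgen deprivation, has been completed.

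State that the first bullet, 4 or more of the first 20 treated, stays in force throughout accrual alongside the second. It should not lapse once 20 men are at risk. As the last column of the simulation table shows, that would lower the chance of suspension below that of the current text.

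With the first bullet kept, the change should not weaken the rule. While fewer than 20 men are at risk and men enter the window in treatment order, every late event lies in the first 20 treated, where 4 already suffice. After that the smaller denominator can only lower the count needed: 5–6 instead of 8 at 40 treated, 7–8 instead of 11 at 51, and 8–9 instead of 12 at 56.

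The cost is one phrase and one sentence. Late-toxicity visits and radiotherapy data are already collected (Sections 4.0 and 18.1), and 16.4.2 allows the rule to be adjusted during the trial. The downside is slightly more temporary suspensions; at a true 5% rate the added chance is close to zero.
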